Eye event: Uveitis (iritis, iridocyclitis)	Grade 1	Discontinue cemiplimab if symptoms persist despite treatment with topical immunosuppressive therapy	
 • Evaluation by an ophthalmologist is strongly recommended. • Treat with topical steroids such as 1% prednisolone acetate suspension and iridocyclitics. 	Symptoms may include (but are not limited to): 
 • Blurred vision • Diffuse erythema and a prominent blush on the sclerae • Dryness of the eyes • Pain • Photophobia 	All attempts should be made to rule out other causes such as metastatic disease, infection, or other ocular disease (e.g., glaucoma or cataracts).
	Grade 2	Discontinue cemiplimab if symptoms persist despite treatment with topical immunosuppressive therapy and do not improve to Grade 1 within the retreatment period OR requires systemic treatment.	
 • Evaluation by an ophthalmologist is strongly recommended. • Treat with topical steroids such as 1% prednisolone acetate suspension and iridocyclitics. 		
	Grade 3–4	Discontinue cemiplimab.	
 • Treat with systemic corticosteroids such as prednisone at a dose of 1-2 mg/kg per day. When symptoms improve to ≤Grade 1, steroid taper should be started and continued over no less than 4 weeks. 		

Event(s)	CTCAE v4.03 Grade	Management/ cemiplimab Dosing	Action/Supportive Care Guidelines	Symptoms ^a	Differential Diagnosis
Hepatic events 
 Hepatitis Hepatitis, Autoimmune 	Grade 1–2	Withhold cemiplimab if there is a treatment-emergent concurrent elevation of ALT and bilirubin that corresponds to an upward shift of 2 or more grades in both parameters.	
 Monitor liver function tests more frequently until returned to baseline values. 	Symptoms may include (but are not limited to): 
 Elevations in: 
 AST >2.5 × ULN ALT >2.5 × ULN Total bilirubin >1.5 × ULN Fever Malaise Upper quadrant abdominal pain 	All attempts should be made to rule out other causes such as metastatic disease, progressive liver disease, viral hepatitis, alternative drug toxicity, infectious causes and/or myositis.
	Grade 3–4	Hold (and consider discontinuation of) cemiplimab when AST or ALT >5.0 times ULN and/or total bilirubin >3.0 times ULN.	
 Consider appropriate consultation and liver biopsy to establish etiology of hepatic injury, if necessary. Treat with high-dose IV glucocorticosteroids for 24–48 hours. When symptoms improve to grade 1 or less, a steroid taper with dexamethasone 4 mg every 4 hours or prednisone at 1–2 mg/kg should be started and continued over no less than 4 weeks. If serum transaminase levels do not decrease 48 hours after initiation of systemic steroids, oral mycophenolate mofetil 500 mg every 12 hours may be given. Infliximab is not recommended due to its potential for hepatotoxicity^b. Several courses of steroid tapering may be necessary as symptoms may worsen when the steroid dose is decreased. 		
Nausea	≤Grade 1	No change in dose	
 Nausea should be treated aggressively, and consideration should be given in subsequent cycles to the administration of prophylactic antiemetic therapy according to standard institutional practice. Patients should be strongly encouraged to maintain liberal oral fluid intake. 		
	Grade 2	Hold until ≤Grade 1. Resume at same dose level. May increase dosing interval by 1 week if it takes more than 4 weeks for toxicities to resolve.			
	Grade 3	Hold until <Grade 2. May increase dosing interval by 1 week for each occurrence. Discontinue if toxicities do not resolve within 12 weeks.			
	Grade 4	Off protocol therapy			

Event(s)	CTCAE v4.03 Grade	Management/ cemiplimab Dosing	Action/Supportive Care Guidelines	Symptoms ^a	Differential Diagnosis
Neutropenia	≤Grade 1	No change in dose	For neutropenia, see general guidelines on hematologic toxicity in Table 2		
	Grade 2	No change in dose			
	Grade 3	No change in dose			
	Grade 4	See Table 2			

Event(s)	CTCAE v4.03 Grade	Management/ cemiplimab Dosing	Action/Supportive Care Guidelines	Symptoms ^a	Differential Diagnosis
Pneumonitis events 
 • Pneumonitis • Interstitial lung disease • Acute interstitial pneumonitis 	Grade 1	Consider hold of therapy. cemiplimab may be continued with close monitoring.	
 • Radiologic findings should be followed on serial imaging studies at least every 3 weeks. • Monitor for symptoms every 2–3 days. • Consider pulmonary consultation and/or bronchoscopy if clinically indicated. 	Symptoms may include (but are not limited to): 
 • Abnormal breath sounds • Chest pain and/or tightness^c • Dyspnea^c • Dry cough • Fatigue • Fever • Hemoptysis 	All attempts should be made to rule out other causes such as metastatic disease, bacterial or viral infection.
	Grade 2	Hold cemiplimab	
To rule out other causes such as infection:
 
 • Consider pulmonary consultation with bronchoscopy and biopsy/bronchoalveolar lavage (BAL). • Consider pulmonary function tests. • Follow radiologic findings on serial imaging studies every 1–3 days 
If the patient is determined to have study drug associated pneumonitis:
 
 • Monitor symptoms daily; consider hospitalization. • Treat with systemic corticosteroids at a dose of 1–2 mg/kg/day prednisone or equivalent. When symptoms improve to Grade 1 or less, steroid taper should be started and continued over no less than 4 weeks. • Treatment with cemiplimab may be resumed if the event improves to ≤ Grade 1 within 12 weeks and corticosteroids have been reduced to the equivalent of methylprednisolone 10 mg by mouth daily or less. Repeat chest imaging monthly as clinically indicated. 
For Grade 2 pneumonitis that improves to ≤Grade 1 within 12 weeks, the following rules should apply:
 
 • First episode of pneumonitis: May increase dosing interval by one week in subsequent cycles. • Second episode of pneumonitis: Discontinue cemiplimab if upon rechallenge the patient develops a second episode of ≥ Grade 2 pneumonitis. 		
	Grade 3–4	Discontinue cemiplimab.	
 • Consider pulmonary function tests with pulmonary consult. • Bronchoscopy with biopsy and/or BAL is recommended. • Treat with IV steroids (2–4 mg/kg per day prednisone or equivalent). When symptoms improve to grade 1 or less, a high-dose oral steroid (1–2 mg/kg prednisone once per day or 4 mg dexamethasone every 4 hours) taper should be started and continued over no less than 4 weeks. • Add prophylactic antibiotics for opportunistic infections. • If IV steroids followed by high-dose oral steroids does not reduce initial symptoms within 48–72 hours, treat with infliximab at 5 mg/kg once every 2 weeks. Discontinue infliximab upon symptom relief and initiate a prolonged steroid taper over 45–60 days. If symptoms worsen during steroid reduction, initiate a retapering of steroids starting at a higher dose of 80 or 100 mg followed by a more prolonged taper and administer infliximab. 		

Event(s)	CTCAE v4.03 Grade	Management/ cemiplimab Dosing	Action/Supportive Care Guidelines	Symptoms ^a	Differential Diagnosis
Renal events 
 • Nephritis • Nephritis autoimmune 	Grade 1	Consider withholding cemiplimab if event does not improve with symptomatic treatment	
 • Provide symptomatic treatment. • Monitor creatinine weekly; when it returns to baseline, resume routine creatinine monitoring per protocol. 	Symptoms may include (but not limited to): 
 • Fatigue • High blood pressure • Increased serum creatinine • Swelling 	All attempts should be made to rule out other causes such as obstructive uropathy, progression of disease, or injury to other chemotherapy agents. A renal consultation is recommended.
• Renal failure	Grade 2	Consider withholding cemiplimab.	
 • Systemic corticosteroids at a dose of 1–2 mg/kg/day of prednisone or equivalent may be indicated. When symptoms improve to Grade 1 or less, corticosteroid taper should be started and continued over at least 1 month. • Consider prophylactic antibiotics for opportunistic infections. • Consider renal biopsy. • If elevations persist >7 days or worsen, treat as Grade 4. 		
• Renal failure, Acute	Grade 3-4	Discontinue cemiplimab.	
 • Renal consultation with consideration of ultrasound and/or biopsy as appropriate. • Monitor creatinine daily. • Treat with systemic corticosteroids at a dose of 1–2 mg/kg prednisone or equivalent once per day. • When symptoms improve to grade 1 or less, steroid taper should be started and continued over no less than 4 weeks. • Discontinue cemiplimab if unable to reduce corticosteroid dose for irAEs to ≤10 mg. • cemiplimab treatment may be restarted and the dose modified as specified in the protocol. 		

Event(s)	CTCAE v4.03 Grade	Management/ cemiplimab Dosing	Action/Supportive Care Guidelines	Symptoms ^a	Differential Diagnosis
Skin events 
 • Dermatitis exfoliative • Erythema multiforme • Stevens-Johnson syndrome • Toxic epidermal necrolysis If considered to be immune related, ≥ Grade 3 or result in dose modification or discontinuation:	Grade 1–2	No change in dose	
 • Symptomatic treatment should be given such as topical glucocorticosteroids (eg, betamethasone 0.1% cream or hydrocortisone 1%) or urea-containing creams in combination with oral antipruritics (eg, diphenhydramine HCl or hydroxyzine HCl). • Treatment with oral steroids is at investigator discretion for Grade 2 events. 		All attempts should be made to rule out other causes such as metastatic disease, infection, or allergic dermatitis.
	Grade 3	Hold cemiplimab.	
 • Consider dermatology consultation and biopsy for confirmation of diagnosis. • Treatment with oral steroids is recommended, starting with 1 mg/kg prednisone or equivalent once per day or dexamethasone 4 mg four times orally daily. When symptoms improve to Grade 1 or less, steroid taper should be started and continued over no less than 4 weeks. 		
	Grade 4	Permanently discontinue cemiplimab.	
 • Dermatology consultation and consideration of biopsy and clinical dermatology photograph. • Initiate steroids at 1–2 mg/kg prednisone or equivalent. When symptoms improve to grade 1 or less, steroid taper should be started and continued over no less than 4 weeks. For any severe (Grade 3-4) irAE, if symptoms worsen or do not improve on adequate corticosteroids within 48-72 hours, consider adding additional immunosuppressive agents (to be selected from agents such as: infliximab, cyclophosphamide, cyclosporine, mycophenolate mofetil). Referral of the patient to a specialized unit for assessment and treatment should be considered		
Thrombocytopenia	≤ Grade 1	No change in dose			
	Grade 2	No change in dose			
	Grade 3	See Table 2			
	Grade 4	See Table 2			

Event(s)	CTCAE v4.03 Grade	Management/ cemiplimab Dosing	Action/Supportive Care Guidelines	Symptoms ^a	Differential Diagnosis
Vomiting	≤ Grade 1	No change in dose	
 Vomiting should be treated aggressively, and consideration should be given in subsequent cycles to the administration of prophylactic antiemetic therapy according to standard institutional practice. Patients should be strongly encouraged to maintain liberal oral fluid intake. 		
	Grade 2	Hold until ≤Grade 1. Resume at same dose level. May increase dosing interval by 1 week if it takes more than 4 weeks for toxicities to resolve.			
	Grade 3	Hold until <Grade 2. May increase dosing interval by 1 week for each occurrence. Discontinue if toxicities do not resolve within 12 weeks.			
	Grade 4	Off protocol therapy			

^a The signs and symptoms may be associated with any of the diagnoses in the associated “Event(s)” column.

^b REMICADE (Infliximab) prescribing information

^c If symptoms indicate possible new or worsening cardiac abnormalities, additional testing and/or a cardiology consultation should be considered.

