	Grade 2	Hold until ≤Grade 1. Resume at same dose level. May increase dosing interval by 1 week if it takes more than 4 weeks for toxicities to resolve.	
 GI consultation and endoscopy is recommended to confirm or rule out colitis for grade 2 diarrhea that persists >1 week or grade 1-2 diarrhea with rectal bleeding (additional guidelines for the treatment of persistent colitis are provided below). Grade 2 diarrhea should be treated with the addition of oral diphenoxylate hydrochloride and atropine sulfate four times daily and budesonide 9 mg daily. Grade 2 diarrhea with diffuse ulceration and bleeding seen on endoscopy may require oral steroids with prolonged taper and represent an increased risk for the development of bowel perforation. Consider prophylactic antibiotics for opportunistic infections. When symptoms improve to Grade 1 or less, steroid taper should be started and continued over no less than 4 weeks. In patients with Grade 2 enterocolitis, cemiplimab should be withheld and anti-diarrheal treatment should be started. If symptoms are persistent for more than one week, systemic corticosteroids should be initiated (eg, 0.5 mg/kg/day of prednisone or equivalent). When symptoms improve to Grade 1 or less, corticosteroid taper should be started and continued over at least 1 month. 		

Event(s)	CTCAE v4.03 Grade	Management/ cemiplimab Dosing	Action/Supportive Care Guidelines	Symptoms ^a	Differential Diagnosis

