Colitis events (continued)	Grade 3–4	
Withhold cemiplimab
 
Discontinue if unable to reduce corticosteroid dose to < 10 mg per day prednisone equivalent within 12 weeks of toxicity
	
 • In patients with Grade 3 enterocolitis, cemiplimab will be permanently discontinued and treatment with systemic corticosteroids should be initiated at a dose of 1–2 mg/kg/day of prednisone or equivalent. When symptoms improve to Grade 1 or less, corticosteroid taper should be started and continued over at least 1 month. Consider prophylactic antibiotics for opportunistic infections. 
For Grade 3–4 diarrhea (or Grade 2 diarrhea that persists after initial steroid treatment),
 
 • Rule out bowel perforation. Imaging with plain films or computed tomography (CT) can be useful. • Consider consultation with gastroenterologist and confirmation biopsy with endoscopy. • Treat with intravenous (IV) steroids (methylprednisolone 125 mg) followed by high-dose oral steroids (prednisone 1–2 mg/kg once per day or dexamethasone 4 mg every 4 hours). When symptoms improve to Grade 1 or less, steroid taper should be started and continued over no less than 4 weeks. Taper over 6–8 weeks in patients with diffuse and severe ulceration and/or bleeding. • If IV steroids followed by high-dose oral steroids does not reduce initial symptoms within 48–72 hours, consider treatment with infliximab at 5 mg/kg once every 2 weeks. Discontinue infliximab upon symptom relief and initiate a prolonged steroid taper over 45–60 days. If symptoms worsen during steroid reduction, initiate a retapering of steroids starting at a higher dose of 80 or 100 mg followed by a more prolonged taper and administer infliximab. CAUTION: infliximab is contraindicated in patients with bowel perforation or sepsis^b. • If symptoms persist despite the above treatment a surgical consult should be obtained. 	
Patients with diarrhea should be carefully monitored for signs and symptoms of enterocolitis (such as diarrhea, abdominal pain, blood or mucus in stool, with or without fever) and of bowel perforation (such as peritoneal signs and ileus). In symptomatic patients, infectious etiologies should be ruled out, and if symptoms are persistent and/or severe, endoscopic evaluation should be considered.
	

Event(s)	CTCAE v4.03 Grade	Management/ cemiplimab Dosing	Action/Supportive Care Guidelines	Symptoms ^a	Differential Diagnosis

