Endocrine events 
 • Hyperthyroidism • Hypophysitis • Hypopituitarism 	Grade 1-2	No change in dose	
 • Monitor thyroid function or other hormonal level tests and serum chemistries more frequently until returned to baseline values. 	Symptoms may include (but not limited to): 
 • Abdominal pain • Abnormal thyroid function tests and/or serum chemistries (Thyroid-stimulating hormone increased [decreased], Free thyroxine increased, Triiodothyronine increased.) • Arrhythmias^c • Cold or heat intolerance • Fatigue • Fever • Headache • Hypotension^c • Loss of appetite • Mental status and/or behavior changes • Nausea and/or vomiting • Unusual bowel habits • Vision disturbances • Weakness 	All attempts should be made to rule out other causes such as brain metastases, sepsis, and/or infection. An endocrinology consultation is recommended.
Endocrine events 
 • Hypothyroidism • Thyroid disorder • Thyroiditis 	Grade 3-4	Hold until on stable replacement dose	
 • Consider endocrine consultation. • Rule out infection and sepsis with appropriate cultures and imaging. • Replacement of appropriate hormones as required. 		
Endocrine events 
 • Adrenal insufficiency • Hypophysitis • Pan-hypopituitarism 	Grade 1-4	Hold until on stable replacement dose	
 • Thyroid hormone and/or steroid replacement therapy to manage adrenal insufficiency. • If Grade 1–2 hypophysitis is considered, pituitary gland imaging should be considered (magnetic resonance imaging [MRIs] with gadolinium and selective cuts of the pituitary can show enlargement or heterogeneity and confirm the diagnosis). • Grade 3–4 hypophysitis with clinically significant adrenal insufficiency and hypotension, dehydration, and electrolyte abnormalities (such as hyponatremia and hyperkalemia) constitutes adrenal crisis. Hospitalization and IV methylprednisolone should be initiated. 		

Event(s)	CTCAE v4.03 Grade	Management/ cemiplimab Dosing	Action/Supportive Care Guidelines	Symptoms ^a	Differential Diagnosis

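### Protocol Appendix 3 gives two incompatible study-drug instructions for Grade 3 enterocolitis and for Grade 1–2 hypophysitis, and leaves the Grade 3–4 renal row ambiguous

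*Protocol*

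**What the plan says.** Appendix 3 gives each event a grade, a study-drug dosing column and a supportive-care column.

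- **Colitis events, Grade 3–4.** The dosing column says to withhold and adds: "Discontinue if unable to reduce corticosteroid dose to < 10 mg per day prednisone equivalent within 12 weeks of toxicity". The supportive-care column of that row says: "In patients with Grade 3 enterocolitis, cemiplimab will be permanently discontinued". One grade lower, the same column reads: "In patients with Grade 2 enterocolitis, cemiplimab should be withheld".
- **Endocrine events.** Hypophysitis is listed in the Grade 1–2 row with the dosing entry "No change in dose". It is listed again, with adrenal insufficiency and pan-hypopituitarism, in a Grade 1–4 row with the entry "Hold until on stable replacement dose". The supportive-care text of the second row speaks of the low grades by name: "If Grade 1–2 hypophysitis is considered, pituitary gland imaging should be considered".
- **Renal events, Grade 3–4.** The dosing column is a bare instruction to discontinue. The supportive-care column adds "Discontinue cemiplimab if unable to reduce corticosteroid dose for irAEs to ≤10 mg" and then "cemiplimab treatment may be restarted and the dose modified as specified in the protocol".

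Section 7.3.2.1 makes Appendix 3 the detailed guidance for immune-related adverse events (irAEs). Table 3 applies to irAEs that Appendix 3 does not address, and both are described as guidelines subject to clinical judgment.

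**The concern.** Appendix 3 is where a site looks when one of these events occurs, and in two places it answers the dosing question in two ways. For low-grade hypophysitis the difference bites at once: one site may continue dosing and another may hold. For Grade 3 enterocolitis both columns stop dosing at onset. The difference comes when the investigator and sponsor decide on resumption under Section 7.3.2, because one column leaves a route back and the other closes it.

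Two things are at stake: uniform patient management across up to about 70 sites, and the meaning of some planned safety output. Adverse events leading to permanent treatment discontinuation are a planned summary (Protocol 10.4.5.1, SAP 5.9.1), and exposure is summarised under SAP 5.7. Both would partly reflect which cell a site happened to read.

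**Working it through.** This is mainly a reading check, so the entries are set side by side.

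| Event and grade | First instruction | Second instruction | Where they part |
|---|---|---|---|
| Enterocolitis, Grade 3 | Withhold; stop only if the steroid taper fails (dosing column) | Permanent stop, unconditional (supportive-care column, same row) | At restart |
| Hypophysitis, Grade 1 | No change (Grade 1–2 row) | Hold (Grade 1–4 row) | At onset |
| Hypophysitis, Grade 2 | No change (Grade 1–2 row) | Hold (Grade 1–4 row) | At onset |

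**Does other text settle enterocolitis?**
- Section 7.3.2 allows resumption by investigator and sponsor, with exceptions for gaps of more than 84 days and for uveitis. Enterocolitis is not named.
- Table 2 gives Grade 3 nonhematological toxicity a route to restart.
- The reasons for permanent discontinuation in Section 7.3.2.2 are expressly not exhaustive.
- Table 3 repeats the conditional hold, but only for irAEs outside Appendix 3.

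None of these resolves the row. Nor is the permanent stop loose wording for a hold, since the same column chose a different verb for Grade 2.

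**Could the hypophysitis overlap come from PDF extraction?** The first two endocrine event lists may be one cell split in reading. Hypophysitis would still sit in both a Grade 1–2 no-change row and a Grade 1–4 hold row.

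**Renal row.** The protocol uses *discontinuation* for temporary stops as well (Sections 6.3, 7.3.1 and 7.3.2), so the row can be read as stop, treat and restart. But the same bare wording for Grade 3–4 uveitis is permanent under Section 7.3.2, and the Grade 4 skin row writes *permanently* outright. The renal cell does not say which sense applies.

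**Table 2.** Its Grade 4 nonhematological row requires discontinuation, while the Grade 3–4 colitis row allows a conditional hold. No sentence says which governs.

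**Illustrative size for enterocolitis.** The plan states no figure to reproduce.
- Planned doses: 5 cycles × 3 + 4 cycles × 4 = 31, every 21 days, so dose *k* falls on day 1 + 21(*k* − 1).
- Section 7.3.2.1 calls onset of diarrhea/colitis at 4 to 6 weeks common, that is, days 28 to 42. Doses given by then: days 1 and 22, so 2.
- Latest restart under the 84-day limit: day 22 + 84 = day 106. Since 1 + 21 × 5 = 106, this is dose 6.
- Doses left under the conditional hold: 31 − 5 = 26, and 26/31 = 84%. Under the permanent stop: 0.
- Sensitivity: the day 43 visit has a ±3-day window. If the third dose is given on day 40, the limit is day 40 + 84 = day 124. The next nominal dosing day is 127 (dose 7), leaving 31 − 6 = 25.

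**The case against.** The strongest reply is that Appendix 3 is guidance, not a rule. Section 7.3.2.1 leaves room for clinical judgment, Section 7.3.2 involves the sponsor in resumption, and irAEs of Grade 3 or above reach the sponsor within 24 hours (Section 9.4.3). This limits the risk for enterocolitis, but guidance with two opposite answers still gives no direction. For Grade 1–2 hypophysitis the grade-based 24-hour trigger does not apply unless the patient had a PI 3-K inhibitor. The endocrinology consultation recommended in the endocrine rows is a safeguard there, though it does not tell the site which dosing entry to follow.

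The enterocolitis sentence could be a stricter sub-rule for one event in a mixed list. However, the dosing column makes no exception, and within the row the sub-rule would stop Grade 3 permanently while Grade 4 kept only the conditional hold. Table 2 would remove that oddity only if it governs, which is not stated.

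On precedence, the text after Table 2 refers the reader to Table 3 and Appendix 3, and some Appendix 3 rows point back to Table 2. This suggests that the other rows stand on their own. It is an inference, since the reference offers only further information.

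Two objections stand in part. The renal row has a coherent sequential reading, so it is only an ambiguity. The dose count is also only an illustration: it counts calendar slots, uses onset timing for diarrhea/colitis in general, and does not show that the remaining doses would be at full dose, since restart may be at a reduced level.

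**Conclusion.** The concern holds for two events and three event-and-grade combinations: Grade 3 enterocolitis, and hypophysitis at Grade 1 and at Grade 2. The conclusion rests on the text alone and needs no assumption about event rates, which the documents do not give. The 26-of-31 figure (25 with an early third dose) assumes onset at weeks 4 to 6, restart at the 84-day limit, no other reason to stop, and missed doses not made up.

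The renal wording and the missing precedence statement are secondary, and the conclusion does not depend on them. The primary ORR test and the sample size are untouched. This should be corrected for patient safety and consistent handling across sites; it does not threaten the primary analysis.

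**What to change.** The sponsor's medical and safety team should reconcile the entries so that Grade 3 enterocolitis and Grade 1–2 hypophysitis each carry one study-drug instruction. Which instruction that should be is a clinical decision for that team. In the same amendment it should:

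- state whether the stop in the Grade 3–4 renal row is temporary or permanent;
- add one sentence on whether Appendix 3 takes precedence over Table 2 for irAEs;
- notify sites.

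Table 3 need not change for these events. The cost is amendment text for three Appendix 3 entries, one precedence sentence and a site notice, with no added procedures, visits or patients.
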